### **Informed Consent:**

In order to recruit or identify subjects, we will screen our patient charts for eligible subjects.

The subject will be fully informed about the study, and will verbalize understanding and voluntarily agree to participate with the guidelines as stipulated in the informed consent. The subject will be informed if he/she can withdraw from the study at any time without loss of benefits. Consent forms will be signed and dated by the subject and by the Principal Investigator or Investigators. The original (with patient's signature) will be maintained per policy. A signed copy of the consent form will be provided to the patient. Informed consent will be obtained prior

to performance of any study procedures. Subjects are given as much time as needed to ask questions and read over the consent.

Subjects will be recruited from the Co-I's own practice. He may get some referrals from his colleagues that work in the same clinic such as [name] and other collaborators. We have included a Waiver of Partial Consent to cover our screening process. The Co-I will identify eligible subjects and alert the coordinator. The coordinator will review all the details of the study with the subject and/or their family. If the subject agrees to participate in the study, they will be screened and then enrolled into the study.

Spanish speakers will be consented using a full Spanish version of the consent. We have Spanish speaking coordinators on staff that can receive consent from Spanish speaking patients.

### **Withdrawal of Patients:**

A Subject may withdraw from the study or be withdrawn from the study at any time and for any reason including but not limited to:

- Non-compliance with the visit schedule
- Non-compliance with the dressing change schedule and/or daily application of AVAZZIA
- Significant protocol violations
- Withdrawal of consent
- Serious adverse event
- Do not satisfy the entry criteria during wound healing process such as presence of infection or need for amputation.

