### **Sample size estimation:**

The estimated number of study subjects is 40. The sample size for the short-term effect (immediate changes in skin perfusion) was estimated to achieve 85% power when comparing to baseline values, using assumed rates of 50% and 10% improvement, respectively. A two-sided test of results in evaluable subjects (qualified for analyses of efficacy on immediate changes on skin perfusion) will provide the specified power at a 5% significance level. Sample size calculations resulted in a requirement for a total of 27 subjects. The sample size for long term benefit was estimated based on our previous study (Najafi et al, Diabetes Sci & Tech, 2017) in which effectiveness of daily use of electrical stimulation to improve balance was examined using a randomized controlled trial model. An effect size of greater than Cohen’s  $d=1.35$  was observed for improvement of mobility post plantar electrical stimulation intervention. In this study we will use a power of 80%, two –tailed t-test, and alpha level of 5% to observe a significant improvement in the intervention group receiving active stimulation compared to sham group (with nonfunctional stimulator), 18 subjects per group is required. Assuming a 10% drop out, the estimated sample size would be 20 subjects per arm. We recognize that this sample size may not be sufficient to validate all primary and secondary outcomes, but would be sufficient to estimate trend and estimate the sample size for follow up study. Upon approval of the sponsor, availability of budget, and based on initial results (first 20 subjects), the sample size may be increased as well.

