### **Schedule of Events**

Visit	Baseline assessment	Follow up					
		#	0	1	2	3	4
Consent & HIPPA forms	X						
Screening (inclusion and exclusion criteria)	X						
Medical & Surgical History	X						
Gram Stain	X					X	
Neuropathy assessment (VPT)	X		X			X	
Immediate Skin Perfusion Pressure Response after one hour of BEST Therapy	X						
BEST Therapy	X	X	X	X	X		
Optional assessments		X				X	
Upper Extremity Test	X					X	
WiFi wound classification	X	X	X	X	X		
Vascular Assessments (SPP and HyperView/Kent Imaging)	X					X	
Wound Photos	X	X	X	X	X		
Thermal Images	X		X			X	
Wound Care (standard of care)	X		X			X	
Adverse Events Reporting	X	X	X	X	X		
Pain Questionnaire (VAS)	X	X	X	X	X		
Heart Rate Variability	X	X				X	
Health Questionnaires (MOCA, FESI, CES-D, PSQI, TSFI, Promis Global)	X					X	
Device Acceptability Questionnaire						X	
Phone Interview							X

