Gram Stain: Bacteria levels will be assessed by collecting a samples and ordering a Gram Stain assessment, which provides an estimate of number of bacteria in the wound. A sample will be collecting before treatment and at 4 weeks.

Wound photo: A digital photo/video will be taken to record wound size.

Thermal Image: A Thermal camera will be used to obtain an image of the wound and observe inflammation.

Definition of Healed Wounds: A wound will be considered “healed” when it is fully epithelialized with no drainage. Only patients with non-infected wound will be recruited. *Infection* will be defined as a patient with three of six clinical signs of infection (erythema, heat, edema, pain, loss of function, purulence) or leukocytosis. We will use the Infectious Diseases Society of America’s Diabetic Foot Infection guidelines to stratify the severity of infection. This guideline stratifies infections into four categories (none, mild, moderate, and severe) based on practical clinical and laboratory findings. Our group has shown this system to be predictive of morbidity.

Health Questionnaires: Quality of Life, Frailty Status, Fear of Falling, Sleep Quality, Depression and Mental Status and Device Acceptability: To evaluate functional status we will use well-accepted questionnaires, PROMIS for Quality of Life, Sleep Quality questionnaire (PSQI), MOCA for cognitive assessment, FES-I for fear of falling, CES-D for depression and TSFI for frailty status. During the last visit, we will ask an acceptability questionnaire.

Upper Extremity Assessment: Investigators will measure the participant's arm motion using a wearable sensor (LegSys, Biosensics LLC, MA USA). This sensor will be placed around the wrist. While being at a comfortable position, the participant will be asked to flex and extend their arm for 20 seconds at a fast speed. They will also be asked to repeat this task but counting backwards as the participants flex and extend their arm (dual task). (Measurement will be done at baseline and visit 4)

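### The protocol permits withdrawal from the study for not using the home device daily, yet describes no record of home use; a cheap improvement of low severity

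*Protocol*

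**What the plan says.** The Protocol, under Withdrawal of Patients, says a participant may leave or be withdrawn from the study "at any time and for any reason including but not limited to" a list of grounds. One is "Non-compliance with the dressing change schedule and/or daily application of AVAZZIA". Others include "Significant protocol violations", missed visits, and no longer meeting the entry criteria, with infection and need for amputation as examples. The withdrawal is from the study, not just from treatment, and no outcome assessment after it is described.

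The treatment is one hour a day at home for up to four weeks, in both arms (Study Design, Aim 2). Participants can change the intensity of the home device (Study Tasks, BEST Therapy). The nearest items to a check on use are:
- the "Device Acceptability Questionnaire" in the Schedule of Events, of which Study Tasks says only "During the last visit, we will ask an acceptability questionnaire";
- the BEST Therapy row of the schedule, which is not described as recording home sessions;
- batteries supplied at visits, with no count described;
- a phone interview, described as recording adverse events.

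On analysis, the Protocol (Statistical analysis) chooses a linear mixed-effect model to cope with missing data points. The SAP uses a linear mixed model, or generalised estimating equations (GEE) for non-normal outcomes. Neither defines an all-randomised set. The only population named is in the sample size section, for the short-term aim: "A two-sided test of results in evaluable subjects". For the randomised comparison that section states "18 subjects per group is required" and then "Assuming a 10% drop out, the estimated sample size would be 20 subjects per arm".

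**The concern.** Unsupervised daily home use is the gap that the Background says this trial fills. Two things follow from the text.

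First, whether someone uses the device is decided after randomisation and may be related to how the wound is doing. If non-use can end follow-up, the participants left at week 4 may no longer be the groups that were randomised.

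Second, with no described record of use, a null or weak result would leave the sponsor less able to judge whether the device did little or was little used. The sample size section intends the data to help size a follow-up study, and delivered exposure bears on that too.

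The two harms are alternatives for any one participant. A non-user who is removed costs outcome data selectively but does not dilute the effect. One who is kept dilutes it but causes no selection.

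**Working it through.** **The plan's own figures.** The dropout step reproduces: 18 / (1 − 0.10) = 20 per arm, so the planned loss is 2 of 20. The 18 per group does not follow from the cited effect. At d = 1.35, two-sided 5% and 80% power, the requirement is 9 per group (normal approximation) or 10 (t-test). That is a separate matter. Here it means only that two effect sizes are worth carrying: d = 0.96, at which 18 per group gives 80% power, and the cited d = 1.35, at which it gives 97.6%.

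**Is home use recorded?** I read the Schedule of Events and all of Study Tasks. No diary, device log, usage download, battery count or adherence question is described. Sessions in the clinic are scheduled; home exposure is not known.

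**Bias from removal.** Assume no true effect, the 2 least adherent of 20 removed from one arm and none from the other, and correlation r between adherence and outcome. The documents give none of these; the 2 is the planned dropout.
- The two lowest of 20 standard normal values have expected values −1.867 and −1.408, which sum to −3.275.
- The mean adherence of the 18 who remain is therefore 3.275 / 18 = 0.182 SD.
- The shift in mean outcome is r × 0.182: 0.3 × 0.182 = 0.055 SD and 0.5 × 0.182 = 0.091 SD.
- Simulated t-tests on completers agree (0.05 to 0.09 SD). Type I error is 5.4% at r = 0.3 and about 6.1% at r = 0.5.
- If 2 are removed from each arm, the shifts cancel.

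**Under the planned models.** These simulations also assume how much of the week-4 change is due to individual slopes (share 0.6 to 0.9).

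| Analysis | Bias (SD) | Type I error |
|---|---|---|
| Complete case | 0.05 to 0.09 | 5.4% to 6.2% |
| Mixed model, weekly data | 0.00 to 0.08 | 4.8% to 5.6% |
| Outcome at baseline and week 4 only | 0.05 to 0.09 | 5.2% to 5.9% |
| GEE, independence working correlation (not stated in the SAP) | 0.04 to 0.10 | 5.1% to 6.2% |

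**What keeping non-users costs.** Assume 2 of 20 active participants are non-users and gain nothing.
- Removed, 18 v 20: power 82% at d = 0.96 and 98% at d = 1.35.
- Kept, 20 v 20: the mean effect becomes 18/20 × d, that is 0.9 × 0.96 = 0.86 or 0.9 × 1.35 = 1.22, with slightly more spread in the active arm. Power is 75% and 96%.

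**The case against.** The case for leaving the text alone has several good parts.

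- **The rule is permissive.** A reader might infer that non-users will be removed and their outcomes lost. The text says only that they may be. The open-ended clause and the protocol-violation ground could cover non-use, but neither is specific to it; only one listed ground names device use.
- **Selection is small and needs an extreme pattern.** Participants and the treating physician are blinded, so removal from one arm only is a worst case. The coordinator does know the allocation, however, and nothing says that withdrawal decisions are made blind.
- **The mixed model helps.** It keeps data collected before withdrawal and is valid if the loss is missing at random. It cannot supply later outcomes. Standard unweighted GEE needs the stronger condition of missing completely at random.
- **Safeguards exist.** Willingness to apply the stimulation is an entry criterion, participants are educated and seen weekly, and batteries are supplied. A non-compliance rule also implies that someone asks about use. A reader might infer that use would go unrecorded in practice; the documents show only that no record is described.
- **A null result was never offered as definitive.** The sample size section says the trial may be too small for all its outcomes and can estimate a trend. A reader might infer that a null could not be separated from non-use at all. That is too strong: the effect of being assigned home use is still estimable, a positive result is interpretable, and a self-reported log would only partly settle the matter.

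A reader might also attach to this rule the large power losses that heavy non-use would bring. Those losses come from non-users who are kept. The rule does not cause them, the fix does not cure them, and the documents give no non-use rate.

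What stands is a stated ground for leaving the study that depends on behaviour after randomisation, with no threshold, no described measurement and no all-randomised analysis set.

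**Conclusion.** The point holds in a limited form. The protocol permits, but does not require, loss of follow-up for non-use, and it describes nothing that would show how much the device was used at home. The resulting bias is probably small: about 0.05 to 0.09 SD for a complete-case comparison if 2 of 20 are removed from one arm only and the adherence–outcome correlation is 0.3 to 0.5, and none if removal is equal. Even 0.09 SD is under a tenth of the d = 0.96 that 18 per group can detect (0.09 / 0.96 = 0.094). The correlation, the one-sided removal and the slope shares are all assumptions.

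The more practical cost is that a null or weak result would be harder to read with home exposure unknown. This is a cheap improvement of low severity, not a threat to the trial's validity.

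**What to change.** In the Protocol's withdrawal section, remove device non-use as a ground for leaving the study. Treat dressing non-compliance, infection and need for amputation in the same way; otherwise similar selective loss stays open through those grounds. Suggested text:

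*Non-use of the device, non-compliance with dressing changes, infection or need for amputation may end device treatment but is not a ground for withdrawal from follow-up, including as a protocol violation. Unless consent is withdrawn, participants continue the existing weekly visits and are analysed in their randomised arm.*

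Issue a one-page daily session log (date, minutes, power setting) with the home device in both arms. The coordinator, who already knows the allocation, collects it at the weekly visits so that the treating physician does not see it. Report use by arm descriptively.

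The cost is a few lines of text, a paper form and one case report form field at visits that already take place. The downsides are minor participant burden, self-report error (so the log only partly explains a null result), and the dilution from keeping non-users shown in the last step of the working. That dilution is the price of estimating the effect of assigned home use.

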### **Statistical analysis:**

Continuous variables are expressed as mean +/- standard deviation (SD). Unpaired t-tests, Mann-Whitney U-tests, and Chi-square-tests will be used for baseline comparison according to the scale of the investigated variable and the distribution of the data. Repeated measures ANOVA tests will be used for examining the effect of intervention in each group after adjusting by age and BMI. Similar test will be used for short-term effect (i.e. changes in skin perfusion immediately after electrical stimulation) and long term benefit (i.e. changes in primary and secondary outcomes after 4 weeks). To account for missing data (prevent entire subject data removal due to lack of a data point), a linear mixed-effect model will be selected instead of univariate general linear model repeated measures analysis. T Chi-square-test will be used for comparing the incident of AE between groups. The effect size to discriminate between groups will be estimated using Cohen's *d* effect size and represented as *d* in the results section. Values ranging from 0.20 to 0.49 indicate small; from 0.50 to 0.79 indicate medium, from 0.80 to 1.29 indicate large, and above 1.30 indicate very large effects. Values less than 0.20 are considered as having no noticeable effect. Spearman correlation of coefficient will be used to examine association between changes in motor parameters and changes in skin perfusion and plantar sensation post intervention. All analyses will be performed using SPSS statistics (version 24; IBM, Armonk, NY, USA) , with a significance level of  $p < 0.05$ .

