**Title: ELECTRICAL STIMULATION AS AN ADJUNCTIVE THERAPY TO ACCELERATE WOUND HEALING
IN PEOPLE WITH PERIPHERAL ARTERIAL DISEASE AND PLANTAR ULCERS & A RANDOMIZED
CONTROLLED TRIAL**

Identifier: NCT03821675

Date: 10/8/2021

Statistical analysis plan

Continuous data were reported with mean \pm standard deviation (SD). Categorical data were presented as count (%). Shapiro-Wilk test was conducted to identify the normal distribution of continuous variables. One-way ANOVA for normally distributed variables or Mann-Whitney U test for non-normally distributed variables was used to estimate differences of mean between control and intervention groups. χ^2 test was used to determine significant level between the groups for categorical variables. The effect size was measured using OR and 95% CI for categorical variables, and Cohen's d to discriminate the difference of primary and secondary outcomes between groups. Outcome changes were assessed over time compared to BL within (ie, time effect) and between (ie, time \times group effect) groups using linear mixed model for normally distributed outcome and generalized estimating equations for non-normally distributed outcome with adjustment for potential confounders. Least significant difference method was used for multiple pairwise comparisons. Pearson and Spearman correlation analysis were performed to assess the relationship between wound or demographics/clinical characteristics, and vascular outcomes. The level of statistical significance was set at $P < .050$. To detect changes in perfusion in individuals with marked limb ischemia, a sub-analysis of patients with moderate to severe peripheral arterial disease (PAD) (ABI < 0.8 or > 1.4 at BL)²⁴ was performed. To detect associated risk comorbidities influencing wound healing in those healers (defined as $\geq 50\%$ of area reduction)²⁵ vs non healers under E-stim, a sub-analysis in the IG was also performed.

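### The protocol's correlation of motor changes with perfusion and sensation changes does not say whether treatment arm is removed; if the arms are pooled, the treatment effects alone can produce an association.

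*Protocol*

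**What the plan says.** The protocol (Statistical analysis) plans Spearman correlation to "examine association between changes in motor parameters and changes in skin perfusion" and in plantar sensation after the intervention. It does not mention arm. The only covariates named in that section belong to the repeated-measures analysis, which is for "examining the effect of intervention in each group after adjusting by age and BMI"; nothing carries them over to the correlation, and arm is not among them.

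The SAP does not list this analysis. It has different pairs: "Pearson and Spearman correlation analysis were performed to assess the relationship between wound or demographics/clinical characteristics, and vascular outcomes". Arm is not mentioned there either, and the SAP's adjustment for confounders is attached to its mixed models and estimating equations.

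The trial expects arm effects on all three quantities. Purpose hypothesises better perfusion and mobility, and Aim 2 hypothesises better plantar sensation under active therapy. Sample size estimation rests on an effect above d = 1.35 that "was observed for improvement of mobility post plantar electrical stimulation intervention" in an earlier study. Background suggests that stimulation improves mobility and balance by way of plantar sensation.

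**The concern.** A plain Spearman coefficient computed over all randomised participants mixes two things: the association between the changes within each arm, and the fact that both changes differ between arms. If stimulation improves mobility and perfusion by separate routes, active participants tend to be high on both and sham participants low on both. The pooled coefficient is then positive with no link inside either arm. For raw vibration-threshold changes the induced sign is negative, taking a lower threshold to mean better sensation; the size is the same.

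The artefact grows with the treatment effects, so it is largest when the device works well on both outcomes. Because Background proposes a route from sensation to mobility, a significant pooled coefficient could easily be read as support for that route when it only restates that the device moved both outcomes.

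**Working it through.** **The plan's own figures.** Neither document gives a figure for the correlation. The numbers used here come from Sample size estimation: "power of 80%, two –tailed t-test, and alpha level of 5"%, d = 1.35 for mobility, "18 subjects per group is required", and 20 per arm after 10% dropout.

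- Dropout: 18 / 0.9 = 20, which reproduces.
- Group size: 18 does not follow from d = 1.35. A two-sided t-test with 80% power needs 9.7, so 10 per group; 18 per group gives about 98% power and corresponds to d of about 0.96. This is a separate matter. It does not alter the check, which uses the planned numbers and a range of effects.

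**Assumptions.** Changes are normal with equal variances, and the within-arm correlation is zero. Allocation is 1:1 (Aim 2). The documents give no between-arm effect on perfusion or sensation, so d2 is varied from 0 to 1.35.

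**Induced correlation.** With equal arms, a difference of d between arms adds d²/4 to the variance of each variable, and the two shifts add d1·d2/4 to the covariance. On the Pearson scale:

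r = d1·d2 / √[(d1² + 4)(d2² + 4)]

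With d1 = 1.35, d1² + 4 = 5.8225:

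- d2 = 0: r = 0
- d2 = 0.2: 0.27 / √(5.8225 × 4.04) = 0.056
- d2 = 0.5: 0.675 / √(5.8225 × 4.25) = 0.136
- d2 = 0.8: 1.08 / √(5.8225 × 4.64) = 0.208
- d2 = 1.35: 1.8225 / 5.8225 = 0.313

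**False-positive rate.** At least 20,000 trials were simulated per setting and tested with pooled Spearman at two-sided 5%. The partial analysis ranks all participants, removes the arm means from the ranks, correlates what remains and tests on N − 3 degrees of freedom. In the table, d1 = 1.35 on mobility.

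| d2 on the other variable | Mean pooled Spearman | 18-20 per arm | About 11 per arm |
|---|---|---|---|
| 0 | 0.00 | about 5% | about 5% |
| 0.2 | 0.06 | about 6% | about 6% |
| 0.5 | 0.14 | 13-14% | about 9% |
| 0.8 | 0.21 | 24-27% | about 16% |
| 1.35 | 0.33 | 51-56% | about 33% |

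With equal, smaller effects on both variables at 18 (20) per arm, the rate is 6.5% (6.3%) at d = 0.5, 12.5% (13.6%) at 0.8 and 19.4% (21.5%) at 0.96.

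Partial Spearman given arm has a mean of about 0 and rejects in 4.8-5.3% of trials in every setting. Correlation within the active arm alone rejects in 4.8-5.4%.

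**The case against.** The strongest reply is that pooling is read into a silence. The same section of the protocol examines the intervention effect in each group, and the SAP runs a sub-analysis within the intervention group, so a within-arm correlation is not excluded. That stands: the documents support saying that the handling of arm is unspecified, and do not support saying that the arms will be pooled. It does not remove the point, because the unstated choice can move the error rate from about 5% to over 50%.

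Other replies also stand in part:

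- **Effect size.** A reader might take the 51-56% as the rate under the protocol's own assumptions. It is not. It needs 1.35 on both variables, and the protocol gives that value for mobility only. With no effect on the second variable there is no inflation. Large effects on two outcomes are also less plausible if sham participants receive the active in-clinic session that Study Tasks (BEST Therapy) describes without reference to arm.
- **Numbers.** Gait, balance and physical-activity tests are optional, and the term motor parameters is not defined, so fewer than 36 to 40 participants may contribute. That lowers the rejection rate but leaves the mean spurious correlation unchanged.
- **SAP.** The SAP omits this correlation, so it may never be run. Its own correlations, "to assess the relationship between wound or demographics/clinical characteristics, and vascular outcomes", are exposed only if they use follow-up values or changes. Baseline values cannot have been shifted by treatment, and a correlation with a baseline variable is not biased in this way.
- **Use of the result.** A reader might infer that the plan intends to claim a mechanism. The protocol says only that association will be examined. Background proposes sensation, not perfusion, as the route to mobility, and Sample size estimation concedes that the trial may be too small to validate every outcome.

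**Conclusion.** The point holds as a conditional one. The handling of arm is not specified. If participants are pooled and the device affects both variables, the Spearman test does not keep its 5% level for the question of whether the changes are linked within a person. With d = 1.35 on mobility, the inflation is negligible when the second effect is 0 to 0.2, moderate at 0.5 and serious from 0.8 upwards. These rates rest on normal changes, equal variances, no within-arm association and assumed effects on perfusion and sensation. The matter concerns a supporting analysis and leaves the between-arm comparisons of primary and secondary outcomes untouched. It is worth correcting because the trial hypothesises the very condition that creates the artefact, and the correction is cheap.

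**What to change.** In the protocol's Statistical analysis section, and in the SAP wherever a correlation uses post-baseline values or changes, state that:

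- correlations are partial Spearman coefficients adjusted for arm, reported with 95% confidence intervals;
- scatter plots show the two arms in different symbols;
- the analysis is exploratory, and the number of participants contributing to each coefficient is given;
- the direction of each measure is stated, so that the sign for vibration threshold is read correctly.

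The SAP should also say whether its wound and vascular correlations use baseline or later values, and whether the protocol's motor correlation is kept or dropped. Partial Spearman is computed on ranks over all participants, so it will be close to, but not identical with, a pooled estimate of separate within-arm coefficients; the plan should name one. Adjusting for arm removes this artefact but does not by itself establish a mechanism.

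The cost is a few sentences and one degree of freedom. No new data are needed, and any correlation already run can be recomputed from the existing data.
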